In this initial visit, subjects will complete baseline questionnaires. This visit will either be in-person at the main hospital in Ann Arbor or performed remotely with the study coordinator. After enrolling in the study, subjects will be given the TEA device and receive instructions on how to use this via ST36. If the participant chooses to have the visit be remote, they will receive the study materials by mail prior to the visit and a pregnancy test supplied by the study team. In

either method of visit, the participant will be given a paid return mailer to give our supplies back. Participants will be subjected to a pregnancy test if they are of child-bearing potential on the day of V1. This will be done in the clinic or self-administered by the subject at home prior to the Zoom appointment. Recommendation to use some form of contraception during the study and birth control options will be discussed. Study participants will use the TEA device for 5 minutes under the supervision of the study coordinator. Subjects will be asked to start the intervention one day after the training received during the initial visit.

III. Home-based treatment period- 4 weeks

TEA will be self-administered at home over two daily treatment sessions of 30 minutes each. TEA will be performed using a device that measures about 4x6 cm (**Figure 2**), and that is programmed by the study team to deliver a specified weak electrical signal. The subject is able to adjust the stimulation output by pressing the “+” or “-“ sign on the device. The stimulation output is adjustable, because the tolerance level varies by individuals and settings will be adjusted based on maximal tolerance. The maximum current output is 10mA. All other parameters, including frequency, pulse width, and time on/time off during the pulsed stimulation, will be fixed. TEA is similar to a transcutaneous electrical nerve stimulation (TENS) unit that is classified by FDA as a non-significant risk device. The device is powered by a small rechargeable battery and the charging will take place only when the device is not in use. This device has been approved for use in two ongoing clinical studies at UoFM by the same investigation team (HUM00189911, HUM00217301).

[figure not shown]

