The treatment will be discontinued if the patient develops an adverse event (discussed under *6. Safety Management*) that requires the treatment to be stopped or at the participant request. Subjects will be allowed to start and continue conventional medical therapy for the duration of the study, including any pain medications. This will be at the discretion of the treating physician. This will allow us to assess the addition of TEA to conventional care. The TEA intervention will be discontinued if the patient gets admitted to hospital or if a surgical or endoscopic procedure is performed during the treatment phase of the study. During the 4 weeks of treatment, subjects will complete pain diaries through RedCap. This will take 2 minutes for completion.

IV. Monitoring phone calls

To assess any potential problems with the TEA device, we will contact participants via telephone within 72 hours of starting treatment and then weekly at 1 week, 2 weeks, and 3 weeks from treatment initiation.

V. Visit 2 (V2), 4 Weeks from V1

During this follow-up period subjects will complete the same set of surveys that was completed during the first visit to assess pain, quality of life, and anxiety or depression. Subjects will also return the TEA device using their return mailer (provided during or prior to visit 1). In the event the device is broken or non-functional, participants will still be requested to return the device.

VI. Visit 3 (V3), at 8 weeks from V1

After subjects finish treatment (4 weeks from V1), they will continue completing daily pain diaries for additional 4 weeks. During this phase, subjects will not receive device stimulation. At 8 weeks from V1, subjects will be asked to complete the same set of surveys completed during visit 1 and 2. These will be completed via RedCap.

VII. Close-out phone call, at end of trial

At the end of the trial, study subjects who enrolled and received TEA will be reached out via a phone call to assess on global impression and acceptability of the treatment.

Outcomes

Primary outcomes

1. Enrollment feasibility: how many patients with CP who are assessed meet eligibility criteria. In addition, of these, how many provide informed consent. Of those who consent, how many meet criteria to participate after the run-in period. Of those who meet run-in period criteria, how many start the intervention (TEA).

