8. Rates of hospital admission for pancreatitis-related hospital admissions [timeframe – 8 weeks from treatment onset]
9. Rates of treatment-related adverse events [timeframe - 4 weeks from treatment onset]
10. Patient global impression of change (PGIC) [timeframe: end of follow-up]: this is a 1-item question that should take less than 1 minute to complete. This question assesses the overall change on pain by using a 7-point Likert scale that ranges from (1) very much improved to (7) very much worse.
11. Modified abbreviated acceptability rating profile [timeframe: end of follow-up]: this is an 8-item questionnaire that should take 2 minutes (Tarnowski KJ, Simonian SJ. Assessing treatment acceptance: the Abbreviated Acceptability Rating Profile. *J Behav Ther Exp Psychiatry* 1992;23:101-6). Each item uses a 5-point Likert scale, including Strongly disagree, Disagree, Neutral, Agree, and Strongly agree. A final score ranges from 0-40, with 40 indicating the highest acceptability possible. This will serve to assess how study subjects perceive the acceptability of the TEA treatment for pain in CP.

Participant timeline

After enrollment, participants will have a 2-week run-in period, where they will complete daily pain diaries. If participants fulfill minimal pain requirements, participants will complete V1 to provide baseline data and will start TEA treatment. Participants will undergo TEA therapy twice a day for 4 weeks. During that time, participants will continue completing daily pain diaries and will 3 weekly phone calls to assess adverse events. After 4 weeks of TEA therapy, the participants will return the device and will complete V2, in which participants will complete questionnaires similar to V1. Participants will then continue completing daily pain diaries for additional 4 weeks, while not receiving the TEA therapy. At completion of those 4 weeks, participants will have closure V3, in which they will provide questionnaires similar to V1 and V2. The total participant's duration in the study is 10 weeks (2 weeks run-in, 4 weeks TEA treatment, and 4 weeks post TEA treatment assessment). At the end of the trial, participants will receive a close-out phone call to assess treatment acceptability.

Table 2: schedule of study visits

Visit ID	V0	V1	Phone call 1	Phone call 2	Phone call 3	Phone call 4	V2	V3 ^	Close-out
Target time	- 2 weeks	0	Within 72h	+1w	+2w	+3w	+4 weeks	+8 weeks	End of trial
Time window	2 weeks	+ 1 week					+ 1 week	+ 1 week	

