Procedure									
Eligibility evaluation	x								
Medical history and demographics	x								
Consent	x								
Pain diary (daily average & worse pain, weekly BPI-SF)	x	x					x	x	
Pain assessment (COMPAT-SF, opioids)		x					x	x	
Quality of life (PROMIS-29)		x					x	x	
Anxiety and depression (HADS)		x					x	x	
Adverse events			x	x	x	x	x		
Pancreatitis-related hospital admissions							x	x	
Patient global impression of change (PGIC)									x
Modified abbreviated acceptability rating profile									x

Recruitment

Participants will be identified using different methods. 1) We will use DataDirect to identify potential participants with chronic pancreatitis who do not have major exclusion criteria and who are actively following at the University of Michigan. This will provide a retrospective list of patients with chronic pancreatitis seen at the University of Michigan in the past 1 year. 2) The study coordinator will also identify potential participants from the list of patients scheduled for clinic visits with [name], [name], or other members of the pancreas clinic. This will be done using MiChart. 3) The study investigators (Drs. [name] and [name]) and physician colleagues seeing patients at the Comprehensive Pancreas Program will refer potential subjects to the study team. The research team will review potential study participants' medical history through the electronic medical record (MiChart) to assess patients' eligibility.

Once a subject is identified through any of the above methods, the subject will be contacted by phone using a phone script or approached in person in the outpatient clinic. The study team will follow a script and go through the pre-screen questions. If the patient is determined to be ineligible via the pre-screen questions they will be excluded from the study and logged as contacted by the study team but ineligible to participate. In doubt, the study investigator will

determine eligibility. If the subject meets eligibility criteria, the subject will be invited to participate in the study. If the subject is interested, an informed consent will be given either in person if the subject is in clinic or mailed for review & signature via eConsent or SignNow.

4. Methods: data collection

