All data will be collected using active and passive methods, including patient interviews, physical examinations, and review of electronic medical records. A trained research coordinator will collect data using standardized forms via RedCap. Research coordinators will follow the manual of operations for all study procedures. All forms will include essential instructions and definitions of variables.

A. Pre-screening form: this will include questions on inclusion and exclusion criteria, pertinent for study eligibility. Initial screening will be based on chart review, in person or telephone patient interview, endoscopic results, and radiologic data that are consistent with the study definition of CP. Screening data will be obtained by the research coordinator before enrollment. This is uploaded into section 8-1.8

B. Pain diary: this will be directly completed by patients. Daily pain scores will be recorded during the 2-week run in period. In those patients who are eligible and are started in TEA, patients will complete the pain diary for 4 weeks during the TEA therapy and will continue for 4 weeks after the intervention is over. The patients will report (a) average pain during the last 24 hours using a VAS, (b) maximal pain during the last 24 hours using a VAS, and (c) weekly BPI-SF (only after intervention started). The survey is uploaded into section 29.1.

C. Baseline form: this will include data on demographics, clinical profile of CP, laboratory biomarkers, radiologic findings, and prior therapeutic interventions, all of which will be recorded from the medical records and by patients filling up a survey. In addition, patients will complete a form pertaining to pain, quality of life, anxiety and depression using the instruments described in secondary outcomes.

D. First follow-up form: this form will be used to assess pain, quality of life, anxiety and depression after the intervention, using the instruments described in secondary outcomes. Adverse events of the intervention will also be recorded in this form. These surveys are uploaded into section 29.1.

E. Second follow-up form: This form will be given to participants during the first follow-up (V2). Subjects will be asked to complete and mail the follow-up questionnaires and diary. This form will be used to assess pain, quality of life, anxiety and depression after the intervention has been discontinued. These surveys are uploaded into section 29.1.

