encrypted and password protected, and the EDC system will comply with the 21 CFR Part 11 requirements for electronic record keeping. All locally-stored data will be on a password-protected computer. Subject charts with medical history and assigned subject numbers will be kept in locked file cabinets stored at the clinical site. Access to charts will be granted only to study investigators. Charts will be kept confidential and will not be shared with any third parties without permission from the subject.

Patients who develop a serious adverse event (SAE), as defined by the Food Drug Administration (FDA) ²⁵, will have the study intervention discontinued, and be managed medically as deemed appropriate by the patient's clinical team. A SAE is defined by the FDA if the AE results in any of the following outcomes: death, a life-threatening AE, inpatient hospitalization or prolongation of existing hospitalization, a persistent or significant incapacity or substantial disruption of the ability to conduct normal life functions, or a congenital anomaly/birth defect. For related, unexpected, serious device events resulting in death and life threatening outcome (per IRBMED guidelines) these will be submitted as soon as possible but within 7 calendar days of becoming aware of the event.

The study team will submit to the reviewing IRB a report of any unanticipated adverse device effect occurring during an investigation as soon as possible, but in no event later than 14 calendar days after the investigator first learns of the effect.

7. Ethics and dissemination

TEA is similar to a transcutaneous electrical nerve stimulation unit that is classified by FDA as a non-significant risk device. Therefore, an investigational device exemption (IDE) for the FDA will not be needed.

The study will require approval by the IRB of the University of Michigan. Any protocol amendments will be communicated to the IRB. Informed consent will be obtained by the study coordinator face to face or by phone from eligible participants or authorized surrogates. If consent is obtained remotely, subjects will be sent a copy of the consent via mail and sign the consent virtually using eConsent or SignNow. Data will be captured in a password protected database. Each subject will be assigned a unique random number, and Protected Health Information will be de-identified after complete data extraction. The final dataset will only be accessible by the primary investigator and data analyst.

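### No adverse-event collection is scheduled for the first device use at V1 or for the period after V2

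*Combined protocol and SAP*

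**What the plan says.** All references are to the combined protocol and SAP.

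- **Outcome.** Section 3, Exploratory outcomes, item 9: "Rates of treatment-related adverse events [timeframe - 4 weeks from treatment onset"].
- **Schedule.** In Table 2 the row "Adverse events" is marked at phone calls 1 to 4 and at V2. It is blank at V0, V1, V3 and close-out. Pancreatitis-related admissions have their own row, marked at V2 and V3.
- **First exposure.** Section 3, II. Visit 1: "Study participants will use the TEA device for 5 minutes under the supervision of the study coordinator". Then: "Subjects will be asked to start the intervention one day after the training received during the initial visit".
- **Calls.** Section 3, IV: "we will contact participants via telephone within 72 hours of starting treatment and then weekly at 1 week, 2 weeks, and 3 weeks".
- **Forms.** Section 4 says of the first follow-up form (V2): "Adverse events of the intervention will also be recorded in this form". It states no such item for the baseline form or for the second follow-up form (week 8).
- **Weeks 4 to 8.** Section 3, VI: "During this phase, subjects will not receive device stimulation".
- **Analysis.** Section 5 reports the proportion of patients with an adverse event due to the intervention. It gives neither a time window nor a denominator.
- **Serious events.** The definition in section 6 includes "inpatient hospitalization or prolongation of existing hospitalization", whatever the cause.

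**The concern.** Tolerability is named in Aim 1, but none of the five primary outcomes measures it directly. Adherence and retention bear on it only indirectly, so the adverse-event proportion is the most direct safety measure in the study.

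That measure has a gap at each end. At the start, section 6 lists skin discomfort or pain, involuntary movements and nausea as possible effects. These can appear as soon as current is applied, and V1 is when current is first applied. At the end, section 6 also lists rash and minor local infection, which can appear after the last session. If either kind of event is not asked about, the proportion may be too low, and the results are meant to shape a larger randomized trial.

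**Working it through.** No figure in the plan needs reproducing here. The sample size of 10 is stated without a derivation and is not in dispute. The check is a timeline followed by short arithmetic.

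**Timeline.** Take V1 as day 0. Home treatment starts on day 1 and lasts 4 weeks, so treatment days are 1 to 28. V2 is 4 weeks from V1, which is day 28.

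| Period | Device use | Scheduled adverse-event collection | Other scheduled safety data |
|---|---|---|---|
| V1 (day 0) | 5 minutes, supervised | none | none |
| Days 1 to 28 | twice daily, 30 minutes | calls 1 to 4, V2 | pancreatitis admissions at V2 |
| After V2 to V3 (week 8) | none | none | pancreatitis admissions at V3 |

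Three things follow.

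1. Day 0 precedes treatment onset, so on a literal reading it lies outside the outcome 9 window. The calls are also timed from the start of treatment. A patient who reacts at V1 and never starts has no call date under that rule.
2. An on-time V2 falls on the last treatment day, leaving zero days of adverse-event follow-up after treatment. V2 may be up to one week late, but the outcome 9 window still closes at 4 weeks.
3. Scheduled collection covers 4 of the 8 weeks after onset, or 5 of 8 if V2 is at the end of its window.

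**Share of exposure at V1.** Home use is 2 × 30 × 28 = 1,680 minutes. V1 is 5 / (1,680 + 5) = 0.3% of planned device time.

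**Effect of one missed event, n = 10.** Exact (Clopper-Pearson) 95% limits:

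- 0/10: upper limit 1 − 0.025^(1/10) = 30.8%.
- 1/10: the upper limit p solves (1 − p)^10 + 10p(1 − p)^9 = 0.025, giving 44.5%. The lower limit is 0.3%.
- The point estimate moves by 1/10, or 10 percentage points.

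**Chance that at least one of 10 patients has an event in an uncovered period.** The documents give no event probability for those periods, so p per patient is assumed over a range, using 1 − (1 − p)^10:

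| Assumed p | Chance of at least one event |
|---|---|
| 1% | 9.6% |
| 5% | 40.1% |
| 10% | 65.1% |
| 20% | 89.3% |

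These are chances that an event occurs, not that it is missed.

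**The case against.** The best defence is that the window matches the exposure. Outcome 9 concerns treatment-related events, and after week 4 the device is returned and no current is given. The protocol also treats V1 and treatment onset as nearly the same point: outcomes timed at 4 and 8 weeks from onset are measured at visits set 4 and 8 weeks from V1. The coordinator is present at V1, in person or remotely. A patient who goes on to treatment can mention a V1 reaction at the 72-hour call or at V2, where no look-back limit is stated. V1 is 0.3% of device time, and the outcome is exploratory in a study declared underpowered for clinical outcomes.

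Much of this stands and limits the point. It does not close the gap. Share of device time is a poor guide to risk at first exposure, and the patient least likely to reach a later contact is the one who could not tolerate V1. Stopping stimulation does not rule out a delayed reaction to the last sessions.

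A reader might also draw four stronger conclusions that the documents do not support:

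- **That a V1 reactor who never starts drops out of the adverse-event denominator.** The denominators restricted to starters belong to adherence and retention (section 5, B and C). The adverse-event line carries no such restriction, the sample of 10 is defined by receiving the device at V1, and analysis is by intention to treat. The denominator is unstated, not wrong. If an analyst did use starters only, the report would be 0/9 (upper limit 1 − 0.025^(1/9) = 33.6%) in place of 1/10.
- **That safety follow-up stops at week 4.** Pancreatitis admissions are collected at V3 and analysed for the off-treatment period. Section 4 includes medical-record review. IRB reporting of unanticipated device effects in section 6 has no week-4 cut-off, although its clock starts only when the team learns of an event and it creates no question after V2.
- **That missing later serious events bias the rate downward.** A hospitalization unrelated to the device would not enter a treatment-related rate even if recorded. Only a delayed related reaction could bias it.
- **That a V1 event is certain to be lost.** It may be lost; the plan does not make it so.

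**Conclusion.** The gap is real and modest. As written, the schedule has no adverse-event collection at first device use or after V2, and the outcome window, read literally, excludes both. What may go unrecorded is a reaction at V1, particularly in a patient who does not start home treatment, and a delayed local reaction. A serious event other than a pancreatitis admission in weeks 4 to 8 is not systematically asked for; that is a gap in safety ascertainment, not in the treatment-related rate.

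One missed related event moves the proportion by 10 percentage points and the exact upper limit from 30.8% to 44.5%. This assumes 10 patients and one such event. The intervals overlap heavily, so the figures also show how imprecise a sample of 10 is. No primary feasibility outcome is affected. The case for changing the plan is that safety ascertainment for Aim 1 improves at little cost, and that an event never asked about cannot reliably be recovered later.

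**What to change.** - In Table 2, mark adverse events at V1 and V3. Add an adverse-event item to the V1 and week-8 forms in section 4.
- Define the outcome 9 window as running from first device use at V1 to V3, and repeat that window in the section 5 analysis line.
- State that the denominator is everyone who had the device applied at V1.
- Report V1, treatment-period and off-treatment events separately. List serious events of any cause apart from the treatment-related proportion, so that the longer window does not mix unrelated events into it.

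**Cost.** A short added item at V1 and in the V3 RedCap survey, a relatedness review of any event reported, and an amendment communicated to the IRB. No V3 interview is described, so the week-8 item would be self-reported and may need a follow-up contact when it is positive. No new visit is needed.

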3. Non-English speaking patients
4. Scheduled for or with a history of pancreatic surgery (e.g. TPIAT, Puestow, Frey, Whipple, other)
5. Currently undergoing or about to start endoscopic therapy with ERCP or EUS
6. Recent history of acute pancreatitis as defined by the Revised Atlanta Classification within a month prior to enrollment
7. Radiologic and clinical findings consistent with symptomatic pseudocyst, wall-off necrosis, infected pancreatic necrosis, or biliary obstruction within the last 6 months
8. Self-reported daily use of opioids for > 12 months for weak opioids (codeine, tramadol and hydrocodone) or > 6 months for strong opioids (other opioids) in the last two years. A similar approach was used in a recent landmark RCT that compared endoscopic therapy vs. surgery in patients with painful chronic pancreatitis.¹⁹
9. Self-reported ongoing illicit drug use or abuse
10. Suspected or diagnosed pancreatic cancer
11. Receiving chemotherapy for cancer
12. Known allergy to adhesive ECG electrodes
13. Patients with bilateral below the knee amputation
14. Patients with lower extremity paralysis
15. Patients are participating in another clinical trial
16. Patients with an implantable electrical stimulation device.

Interventions

I. Run-in period: 2 weeks (V0)

After initial screening (V0 – virtual or in person) and after the consent form is signed, subjects that fulfill eligibility criteria will be invited to participate to the study.

All eligible subjects will then complete a pre-enrollment run-in period of 2 weeks. Over this run-in period, subjects will be asked to complete a diary with information on daily severity of abdominal pain. Subjects will rate their worst daily abdominal pain intensity over the past 24 hours by putting a mark on a visual analogue scale (scoring 0-10), where 0 represents “no pain” and 10 represents the “worst imaginable pain.” Subjects with abdominal pain severity of 4 or greater for at least 5 days in this run-in period will be invited for a site visit to start the intervention (V1). Subjects who don’t qualify for this criterion will not be invited to receive the intervention. A similar approach has been used in a prior RCT evaluating the role of antioxidants for pain in CP.²⁰ Surveys will be completed via RedCap.

II. Visit 1 (V1)

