2. Adherence: of those who start the intervention, how many adhere to the intervention as prescribed. The time of the day and duration of each TEA administration will be automatically recorded by the TEA device.
3. Retention feasibility: how many patients who start the intervention complete follow-up visit at week 4 and return complete follow-up questionnaires at week 8.
4. Visits duration: how long does it take to complete visits 1 and 2.
5. Data collection feasibility: how many patients complete all the surveys. In addition, we will calculate the proportion of study surveys that are completed per protocol

Exploratory outcomes

1. Pain diary records [timeframe: daily from 2-week run-in period until 8 weeks from treatment onset]: this will be used to measure daily pain experience on an 11-point visual analogue scale (VAS). The recording of daily pain scores will be started during the 2-week run-in period and will end 8 weeks after the intervention is over. Subjects will mark a point along a scale (from no pain [0] to worst imaginable pain [10]) on the VAS related to (a) average pain and (b) worst pain during the last 24 hours on two separate entries. This will be done at a fixed time of the day chosen by the participant. We will measure the change of average and worst pain from baseline to 4 weeks and 8 weeks post-treatment.
2. Brief Pain Inventory—Short Form (BPI-SF) [timeframe - weekly from baseline until 8 weeks from treatment onset]: The BPI-SF is a validated self-reported tool that evaluates pain severity and pain interference with daily activities at the time of assessment. A total of 4 pain intensity items (worst, least, average, and current pain) are rated on an 11-point numerical rating scale (0 = no pain, 10 = worst possible pain). The pain interference subscale includes 7 items evaluating the impact of pain on sleep, mood, walking ability, general activity, work, relationships, and enjoyment of life over the past 24 hours rated on an 11-point scale from 0 = does not interfere to 10 = completely interferes. Possible scores for pain severity range from 0 to 40 (higher scores reflect more severe pain); possible scores for pain interference range from 0 to 70 (higher scores reflect more pain interference with daily life).

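### The BPI-SF analysis needs a pre-treatment value that one part of the protocol excludes, and two BPI-SF interference rows analyse severity by mistake

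*Combined protocol and SAP*

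**What the plan says.** The timing of the BPI-SF is given in four places.

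- Section 4 (Methods: data collection), item B, Pain diary: after the two daily VAS ratings, the diary includes "weekly BPI-SF (only after intervention started".
- Exploratory outcomes, item 2: the timeframe is "weekly from baseline until 8 weeks from treatment onset".
- Table 2: the diary row, which names the weekly BPI-SF together with the daily ratings, is marked at V0, V1, V2 and V3. V0 is two weeks before V1, and Interventions, II, starts treatment the day after the V1 training. Both V0 and V1 are therefore before treatment.
- Section 5, Exploratory endpoints: the BPI-SF severity and interference blocks each use the run-in period as baseline and compare the last treatment week with it.

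Three other places bear on the question. Interventions, I, says of the run-in that "subjects will be asked to complete a diary with information on daily severity of abdominal pain", and does not mention the BPI-SF. Interventions, II, says "In this initial visit, subjects will complete baseline questionnaires" without listing them. Section 4, item C (Baseline form), includes a pain form but names no instrument; it points to secondary outcomes, a heading the protocol does not have.

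In section 5, the last two rows of the BPI-SF interference block refer to pain severity.

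For the daily ratings, Exploratory outcomes, item 1, plans change from baseline in average and worst pain at a 4-week and an 8-week time point. Its timeframe is "daily from 2-week run-in period until 8 weeks from treatment onset", yet its text says that recording "will end 8 weeks after the intervention is over". Interventions, VI, says that after treatment "they will continue completing daily pain diaries for additional 4 weeks".

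**The concern.** A change from baseline needs a value recorded before treatment. Item B, taken at its word, keeps the BPI-SF out of the diary until treatment has begun, while section 5 analyses a run-in BPI-SF. If staff follow item B and nothing else captures the instrument, the planned BPI-SF change cannot be estimated. The interference items ask about the past 24 hours, so a later form cannot recover the run-in state. The multiple imputation planned in section 5 cannot help either: if no participant has a baseline BPI-SF, there are no observed values from which to model it.

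The interference rows are a separate matter. Followed as written, they repeat a severity comparison and never compare interference after treatment with interference in the last treatment week.

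The schedule also decides which BPI-SF forms count as completed per protocol in primary outcome E (data collection feasibility).

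**Working it through.** The plan gives no figure that depends on this timing, so the check sets the text side by side and counts rows.

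**Pre-treatment BPI-SF forms implied by each source**

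| Source | Before treatment |
|---|---|
| Section 4, item B | none in the diary |
| Exploratory outcomes, item 2 | at least one, at baseline |
| Table 2, diary row | marks at V0 and V1 |
| Section 5, BPI-SF blocks | at least one, in the run-in |

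**Rows affected.** Each BPI-SF block in section 5 has 5 means, 2 mean differences and 2 tests: 5 + 2 + 2 = 9. Two blocks give 2 × 9 = 18. The rows that need a baseline are, per block, the baseline mean, the difference between the last treatment week and baseline, and its test: 2 × 3 = 6.

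**Three readings**

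| Reading | Baseline BPI-SF | Consequence for the 18 rows |
|---|---|---|
| 1. Item B governs and the item C form omits the BPI-SF | none | 6 cannot be computed or imputed |
| 2. The item C form includes the BPI-SF at V1 | one V1 value | all 18 have data, but 6 rest on V1 and not on the run-in baseline named |
| 3. Exploratory outcomes, Table 2 and section 5 govern | run-in value | all 18 have data as named; the item B restriction is the error |

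**Interference block.** Rows 8 and 9 of 9 (the difference between the period after treatment and the last treatment week, and its test) name severity. They match the last two rows of the severity block, so 2 of 9 interference rows repeat another analysis. These are not among the 6 baseline rows.

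**Daily pain ratings.** The worst-pain and average-pain blocks list means for the run-in and for week 8, but no difference between them. Set against Exploratory outcomes, item 1, 2 mean differences are absent, one per rating. The COMPAT-SF, opioid dose, quality of life and HADS blocks all include the corresponding contrast, which suggests an oversight.

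**Length of follow-up.** Item 1's own timeframe ends 8 weeks from treatment onset. With 4 weeks of treatment, that leaves 8 − 4 = 4 weeks afterwards. Interventions, VI, the Participant timeline and section 4, item B, all agree. The sentence that gives 8 weeks after the intervention is a slip.

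**The case against.** The strongest reply is that item B is the outlier. Three places plan a BPI-SF before treatment, and item B describes only the diary. A BPI-SF on the V1 form followed by weekly diary forms would satisfy Exploratory outcomes, item 2, Table 2's V1 mark, and items B and C together. The V0 mark may be meant for the VAS ratings that share the row. This largely stands, and it is why Readings 2 and 3 must be given alongside Reading 1. It does not remove the conflict: item C does not name the BPI-SF, and a V1 value is not the run-in baseline in section 5.

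A reader might go further in four ways that the documents do not support.

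- That the baseline BPI-SF will be missing. This holds under Reading 1 only, and the survey as built is not available to settle it.
- That the run-in description shows the BPI-SF was not intended there. That text asks for worst pain and omits average pain, which other sections place in the run-in. It is incomplete, so its silence shows little.
- That a V1 baseline is compromised because at V1 "Study participants will use the TEA device for 5 minutes under the supervision of the study coordinator". Interventions, II, mentions the baseline questionnaires first and starts the intervention a day after that training, so V1 is before treatment on the protocol's own terms.
- That primary outcome E is materially distorted. Any percentage would need assumptions about which forms are issued and counted that the documents do not give. What stands is that the set of forms counted must be stated.

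It is also fair to say that the daily-rating points are editorial and add no weight to the BPI-SF conflict.

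**Conclusion.** The contradiction is confirmed from the text. Its consequence depends on the reading: 6 of 18 BPI-SF rows without data, 6 of 18 against a baseline other than the one named, or none affected. Which applies cannot be determined here. The error in the interference block is certain under every reading and affects 2 of 9 rows. The 2 missing week-8 differences and the follow-up slip are smaller.

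This is worth correcting, at low priority. The affected pain endpoints are exploratory, in a pilot of 10 that the protocol itself calls underpowered for clinical outcomes. A reader might infer that Aim 2 fails without a BPI-SF baseline. It does not: the VAS ratings are taken in the run-in, and COMPAT-SF and PROMIS-29, which has a pain interference domain, are taken at V1.

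**What to change.** Check which reading the built survey follows. If data collection has not begun, secure at least one BPI-SF before treatment by either route:

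- delete the restriction in section 4, item B, and collect the BPI-SF in the run-in, which keeps Exploratory outcomes, Table 2 and section 5 as they are; or
- name the BPI-SF in section 4, item C, as part of the V1 form, and redefine the baseline in both BPI-SF blocks of section 5 as the V1 value.

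Then align Exploratory outcomes, item 2, Table 2, section 4, items B and C, and section 5. State that outcome E counts only the forms in that agreed schedule. If data were already collected with no pre-treatment BPI-SF, drop the 6 baseline rows.

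Under any route:

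- change severity to interference in the last two rows of the interference block;
- add the week 8 versus baseline mean difference for worst and for average pain, as description without tests;
- correct the follow-up wording in Exploratory outcomes, item 1, to match its own timeframe.

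The cost is about one short form per treated participant, so roughly 10 forms at the planned size. The run-in route needs somewhat more, because consented subjects who do not qualify would also complete it. The rest is wording and 2 descriptive rows.
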